7. PHARMACEUTICAL INFORMATION

7.1 Gabapentin

Please refer to the FDA-approved package insert for additional information.

a. Description – Anticonvulsant, Miscellaneous; GABA Analog

b. Pharmaceutical Data (as taken from UpToDate) –

Absorption: Variable, from proximal small bowel by L-amino transport system; saturable process; dose-dependent

Distribution: $V_d: 58 \pm 6 \text{ L}$; CSF concentrations are ~20% of plasma concentrations

Protein binding: <3%

Metabolism: Not metabolized

Bioavailability: Inversely proportional to dose due to saturable absorption:

Immediate release:

900 mg/day: 60%

1,200 mg/day: 47%

2,400 mg/day: 34%

3,600 mg/day: 33%

4,800 mg/day: 27%

Half-life elimination:

Adults, normal: 5 to 7 hours; increased half-life with decreased renal function; anuric adult patients: 132 hours; adults during hemodialysis: 3.8 hours

Time to peak: Adults: 2 to 4 hours.

Excretion: Proportional to renal function; urine (as unchanged drug)

Clearance: Apparent oral clearance is directly proportional to CrCl.

c. Administration – Orally

d. Storage and Stability - : Store vials at room temperature and protect from light.

e. Supplier – Gabapentin is commercially available.

8. STUDY CALENDAR

The institutional review board (IRB) approval process is expected to be completed by March of 2017. The trial will start accrual of patients subsequently. Given the typical volume of patients treated at our institution, it is expected to take 1-1.5 years to accrue the required 60 patients to complete this study. Patients will be followed up until the first follow-up after completion of radiation treatment (6 weeks). The trial is expected to conclude January of 2019 with data analysis and reporting to take place subsequently.

9. STATISTICAL CONSIDERATIONS

9.1 Study Endpoints/ Analysis Plan

9.1.1 Primary endpoint

The primary endpoint is change in quality of life and pain, as measured by the Patient-Reported Oral Mucositis Symptoms (PROMS) scale over the entire study period. This will be measured at baseline and weekly during clinic visits. Additional measurements will be obtained at 6-weeks (first follow-up) from the time of radiation treatment completion.

The PROMS scale consists of 10 questions on a visual analogue scale of 100-mm lines addressing oral functions affected by oral mucositis.[13] This questionnaire has been validated in patients undergoing radiation treatment for head and neck cancers and correlates well with clinician determined scores of mucositis.[14]

Repeated measures analysis of variance (ANOVA) will be used to determine if there was a significant difference between the mean PROMS scores of the two groups over the entire study period, and t-tests will be used to examine if there was a difference in the PROMS scores for the two groups at each week of the study period.

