4.5 Assignment of interventions

4.5.1 Allocation sequence generation

Separate randomization lists will be produced by a statistician for current smokers as well as for former/ non-smokers with a goal of 1:1 allocation to both treatment arms.

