9.1.2 Sample size/ Justification of Number of Subjects

Based on reported means and standard deviation of PROMS scores of patients undergoing radiation treatment, a total of 60 patients will be required to evaluate a 16% reduction in PROMS score at week 7 (final week) of radiation treatment, with $\alpha = 0.05$ and power = 80%. This assumes a 10% dropout rate.

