9.2.4 Opioid Use

Patients with at least 1 reported administration of opioid analgesic will be considered to have received opioid analgesics. The total dose of opioid analgesics will be the sum of all opioid analgesic administrations that have been converted to morphine equivalents (see Appendix II). Use of opioid analgesics will be assessed for a 24-hour period before completing the assessment weekly during radiation. The relationship between analgesic use and treatment-related pain will be evaluated using the general linear model with (at minimum) stratification, treatment arm, and compliance.

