9.2.6 Other Quality of Life Metrics

Patients will be asked to complete the FACT-HN and PRO-CTCAE quality of life forms (see Appendix). The FACT-HN will be assessed at baseline and at the 7-week (final week) of radiation. The PRO-CTCAE will be assessed at baseline and weekly with the PROMS scale.

The change in scores from baseline to the 6-week follow-up timepoint will be used for analysis.

All assessments are summarized in Table 1.

Table 1. Subject assessments.

| Parameters | Prior to Study Therapy | Weekly During Radiation Therapy | At First Follow-up (6-weeks post completion) |
|---|------------------------|---------------------------------|--|
| History and Physical ^a | X | | X |
| Performance status ^a | X | | X |
| Creatinine | X | | |
| PROMS Score ^b | X | X | X |
| HN-PSS Score ^a | X | X | X |
| FACT H&N ^b | X | | X |
| Weight | X | X | X |
| Daily opioid use (in morphine equivalents) ^a | X | X | X |
| Assess if feeding tube has been placed ^a | X | X | X |
| CTCAE and other adverse events ^a | X | X | X |
| PRO-CTCAE questionnaire ^b | X | X | X |

^a Physician or evaluator reported.

^b Patient reported.

REFERENCES

1. Starmer, H.M., et al., *Effect of gabapentin on swallowing during and after chemoradiation for oropharyngeal squamous cell cancer*. Dysphagia, 2014. **29**(3): p. 396-402.
2. Chaturvedi, A.K., et al., *Human papillomavirus and rising oropharyngeal cancer incidence in the United States*. Journal of Clinical Oncology, 2011. **29**(32): p. 4294-4301.
3. Marur, S. and A.A. Forastiere, *Head and neck cancer: changing epidemiology, diagnosis, and treatment*. Mayo Clin Proc, 2008. **83**(4): p. 489-501.
4. Pignon, J.-P., et al., *Meta-analysis of chemotherapy in head and neck cancer (MACH-NC): an update on 93 randomised trials and 17,346 patients*. Radiotherapy and Oncology, 2009. **92**(1): p. 4-14.
5. Trott, A., et al., *TAME: development of a new method for summarising adverse events of cancer treatment by the Radiation Therapy Oncology Group*. Lancet Oncol, 2007. **8**(7): p. 613-24.
6. Moslemi, D., et al., *Management of chemo/radiation-induced oral mucositis in patients with head and neck cancer: A review of the current literature*. Radiother Oncol, 2016. **120**(1): p. 13-20.

7. Epstein, J.B., et al., *Neuropathic and nociceptive pain in head and neck cancer patients receiving radiation therapy*. Head & neck oncology, 2009. **1**(1): p. 1.

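### The primary PROMS analysis leaves the role of baseline open and uses neither baseline PROMS nor the smoking stratum: valid as planned, but cheap to sharpen

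*Combined protocol and SAP*

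**What the plan says.** Section 9.1.1 opens: "The primary endpoint is change in quality of life and pain, as measured by the Patient-Reported Oral Mucositis Symptoms (PROMS) scale", taken over the whole study. On collection it says: "This will be measured at baseline and weekly during clinic visits", with one more measurement at the 6-week follow-up. The repeated measures ANOVA is to look for a "difference between the mean PROMS scores of the two groups over the entire study period". In addition, "t-tests will be used to examine if there was a difference in the PROMS scores for the two groups" week by week. No covariate and no stratum is listed for either analysis.

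Section 4.5.1 stratifies the allocation: "Separate randomization lists will be produced by a statistician for current smokers as well as for former/ non-smokers". The only model that mentions the stratification is the secondary one for opioid use in 9.2.4, a general linear model "with (at minimum) stratification, treatment arm, and compliance".

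Two secondary outcomes have a rule for baseline. Section 9.2.3 compares percent weight change from baseline, and 9.2.6 says: "The change in scores from baseline to the 6-week follow-up timepoint will be used for analysis". That sentence stands under the other quality-of-life metrics, so it does not settle the matter for PROMS.

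Section 9.1.2 sizes the trial at one visit: "a total of 60 patients will be required to evaluate a 16% reduction in PROMS score at week 7", with 5% alpha, 80% power and 10% dropout.

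**The concern.** The endpoint is named as a change, but the test is on scores. Three analyses fit the text: subtract baseline from each later score, adjust for baseline as a covariate, or treat baseline as one more level of the repeated factor. A fourth, leaving baseline out, also fits the weekly t-tests. These analyses do not have the same power, and one of them mixes a visit at which no treatment effect can exist into the arm comparison. With about 54 evaluable patients planned for 80% power there is little slack, and if the text stays as it is the choice will be made at analysis.

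The second part concerns precision. Baseline PROMS and smoking status will both be on file for each patient. If either predicts later PROMS, leaving it out gives away precision that costs nothing to collect.

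**Working it through.** **1. The plan's own figure.** 60 × 0.90 = 54 evaluable, 27 per arm. The PROMS mean and SD are not printed, so 60 can be neither confirmed nor refuted. Solving backwards, with two-sided 0.05 assumed because sidedness is not stated: (1.960 + 0.842) × √(2/27) = 0.76 SD by the normal approximation, or d = 0.777 by the noncentral t with 52 df. That corresponds to an SD of 0.16/0.777 = 0.21 of the control mean if 16% is relative, or 16/0.777 = 20.6 points if it means 16 points on a 0–100 scale. I use d = 0.777, which puts the unadjusted week-7 comparison at 80.0%.

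**2. Week 7 under each role for baseline.** Let r be the correlation of baseline with week-7 PROMS and s the ratio of baseline SD to week-7 SD. Neither is in the documents. With the unadjusted score variance set to 1:

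- change score: 1 + s² − 2rs, which is 2(1 − r) when s = 1
- adjusted for baseline: 1 − r²

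Power comes from the noncentral t with noncentrality 0.777/√(variance × 2/27). At r = 0.3 and s = 1 the noncentrality is 0.777/√(1.4 × 2/27) = 2.41 for the change score and 0.777/√(0.91 × 2/27) = 2.99 for the adjusted comparison, against 2.85 unadjusted.

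| r | Raw score | Change score (s = 1) | Adjusted, formula (50 df) | Adjusted, simulated |
|---|---|---|---|---|
| 0 | 80% | 51% | 79.9% | 79.0% |
| 0.2 | 80% | 60% | 81.5% | 80.9% |
| 0.3 | 80% | 66% | 83.5% | 83.0% |
| 0.5 | 80% | 80% | 89.8% | 89.3% |

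The simulated column adjusts for baseline and a non-prognostic smoking stratum and includes chance covariate imbalance (100,000 trials per cell, Monte Carlo error about ±0.25 points; 30% current smokers, baseline independent of smoking and blocks of 4, all assumed).

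The change-score penalty depends on s. With s = 0.5 and r = 0.3 the variance is 1 + 0.25 − 0.30 = 0.95 and power is about 82%. The change score beats the raw score only when s < 2r. Apart from the small loss of df, adjustment is never worse than the change score, because (1 + s² − 2rs) − (1 − r²) = (s − r)² ≥ 0.

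**3. Adding the smoking stratum.** Power adjusted for baseline and stratum minus power unadjusted, in points, in the same simulated trials. Ranges cover blocked and unblocked lists; 4.5.1 does not mention blocks.

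| Variance explained by smoking | r = 0 | r = 0.2 | r = 0.3 | r = 0.5 |
|---|---|---|---|---|
| 0% | −1.8 to −0.9 | −0.1 to +0.7 | +2.0 to +2.9 | +8.7 to +9.3 |
| 5% | +0.4 to +0.5 | +2.0 to +2.2 | +4.3 | +10.7 to +11.0 |
| 10% | +2.1 to +2.6 | +3.8 to +4.1 | +5.7 to +6.3 | +11.8 to +12.8 |

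At r = 0.3 with non-prognostic smoking the variance ratio is 0.0747/0.0693 = 1.078 (blocked) or 0.0746/0.0708 = 1.054 (unblocked). That is worth 54 × 0.054 to 54 × 0.078, or 2.9 to 4.2 evaluable patients.

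**4. Validity.** At r = 0.3, the size of the unadjusted test with blocked lists is 0.049, 0.044 and 0.039 when smoking explains 0%, 5% and 10% of variance. With unblocked lists it is 0.049 to 0.050. The adjusted test stays at 0.048 to 0.050. Nothing is inflated.

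**5. The whole-period comparison.** Seven weekly visits and the follow-up give 8 post-baseline visits. If the arm effect is D at each of them and zero at baseline, averaging over all nine gives 8D/9. As an illustration only, take inter-visit correlation 0.7, r = 0.3, D = 0.5 SD and equal SDs:

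| Role of baseline | Effect | Variance | Power |
|---|---|---|---|
| Counted as a level | 0.444 | (64 × 0.7375 + 1 + 4.8)/81 = 0.654 | 51% |
| Left out (post-baseline mean) | 0.5 | (1 + 7 × 0.7)/8 = 0.7375 | 56% |
| Subtracted | 0.5 | 0.7375 + 1 − 0.6 = 1.1375 | 39% |
| Covariate | 0.5 | 0.7375 − 0.09 = 0.6475 | 61% |

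**The case against.** The best case for the plan is that an unadjusted comparison after randomisation is valid, that the gain from adjustment is hypothetical, and that it may be nil. Baseline precedes radiation, and PROMS items 2 to 9 ask about limitation from mouth sores (Appendix III), so baseline scores may be low and weakly related to week 7. At r = 0 with non-prognostic smoking, adjustment loses power. The gains of 9 points and more need r = 0.5, which nothing in the documents supports. All of this stands, and it rules out presenting the omission as a sizeable loss.

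A reader might also infer that 9.1.1 never says which ANOVA term is primary. That goes too far. The sentence describes a difference between the two groups' mean scores over the whole period, which in words is the arm main effect; it does not point to arm-by-week. What stays open is whether baseline is inside that mean and how the mean relates to the word 'change'.

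Nor is the primary analysis an exception within this plan. The Wilcoxon test in 9.2.3 and Fisher's test in 9.2.5 are unadjusted too, 9.2.2 promises to report change in PSS without a method, and 9.2.4 gives baseline opioid use no role. The model in 9.2.4 that includes stratification relates analgesic use to pain and is not a plain comparison of arms. The contrast with the secondary outcomes is therefore only partial.

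Finally, the firmest power figures are for week 7, while the primary test covers the whole period. That is fair: the whole-period figures are an illustration under assumed correlations. The dilution to 8/9 does not depend on those correlations, only on the visit count and a constant effect.

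**Conclusion.** The point holds as a cheap improvement. Section 9.1.1 calls the endpoint a change, tests mean scores, and does not say how baseline enters; baseline PROMS and the smoking stratum are both unused. The documents do not support a claim of bias, of an invalid test or of a wrong sample size. If smoking is prognostic and the lists are blocked, the planned test is slightly conservative.

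The open choice is the larger part. At an assumed r of 0.3, week-7 power runs from about 66% (change score, equal SDs) through 80% (raw score) to about 83% (adjusted). The low end rises if baseline scores are much less variable than week-7 scores. The gain over the plain score is conditional: about 0 to 3 points at r of 0.2 to 0.3 with non-prognostic smoking, more only if r or the smoking effect is larger. These figures rest on 27 evaluable per arm, two-sided 0.05 and correlations that the documents do not give.

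**What to change.** In 9.1.1, model the post-baseline PROMS scores in a repeated-measures model with arm, week, arm-by-week, baseline PROMS as a covariate, and smoking stratum (current versus former or never). State that the primary estimate is the baseline-adjusted arm difference averaged over the study period, and that this is how 'change' is handled. Take the weekly contrasts from the same model, including week 7, on which 9.1.2 sizes the trial. Baseline-by-week terms are optional. Settle this before the study is unblinded under 4.5.4.

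The cost is wording and two more model parameters, with no added patients, visits or data. The downside is about 1 point (blocked lists) to 2 points (unblocked) of week-7 power if neither variable is prognostic. Break-even is at r of about 0.15 to 0.2 if smoking does not matter.

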4.3 Protocol Treatment

[figure not shown]

Figure 1: Treatment schema, as described below.

4.3.1 Arm 1

Patients will receive a placebo along the same dosing schedule as the experimental arm (patients randomized to placebo will take the same number of capsules as those assigned to gabapentin).

This will also include standard supportive care for treatment-related pain and mucositis as needed during concurrent chemotherapy and radiation treatment, consisting of the following:

- Viscous lidocaine 2% oral solution
- Oral liquid or solid opioid medications- e.g., morphine, oxycodone. These will be introduced and titrated at the discretion of the treating physician when the patient-reported pain score is ≥ 4 on a 0-10 scale.

4.3.2 Arm 2

Gabapentin will be initiated at a dose of 300 mg to be taken at bedtime of the night prior to the first radiation treatment. During week 1, the dose will be 300 mg three times a day for a total daily dose of 900 mg. Starting week 2, the dose will be 600 mg taken 3 times per day for a total daily dose of 1800 mg. This will continue until one week after the end radiation treatment (week 8). Therapy will then be titrated down to 300 mg three times a day for 1 day, and then discontinued all together. The standard supporting care for treatment-related pain and mucositis described above will also be included.

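### The primary PROMS mean covers the whole study period, so a score about 5 weeks off drug, and possibly the pre-drug baseline, is averaged with the on-treatment weeks

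*Combined protocol and SAP*

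**What the plan says.** Section 9.1.1 defines the primary endpoint as change in quality of life and pain "as measured by the Patient-Reported Oral Mucositis Symptoms (PROMS) scale over the entire study period". On timing it says "This will be measured at baseline and weekly during clinic visits", and then "Additional measurements will be obtained at 6-weeks (first follow-up) from the time of radiation treatment completion". Table 1 marks PROMS in all three columns: before therapy, weekly, and at first follow-up. The primary analysis is a repeated measures ANOVA for a "significant difference between the mean PROMS scores of the two groups over the entire study period", with t-tests at each week alongside it. Section 8 follows patients to the 6-week visit.

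Under section 4.3.2, gabapentin starts the night before the first radiation treatment and continues until one week after radiation ends. Then: "Therapy will then be titrated down to 300 mg three times a day for 1 day, and then discontinued all together". Section 4.3.1 puts placebo on the same schedule. Section 7.1 gives the elimination half-life as "Adults, normal: 5 to 7 hours; increased half-life with decreased renal function".

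The title places the question during treatment, and section 9.1.2 sets the sample size on a 16% reduction at week 7, the last week of radiation. No section says which visits enter the ANOVA mean, or whether baseline is a level of the repeated factor or a covariate.

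**The concern.** The averaging window and the trial's question do not match. In an equally weighted whole-period mean, the follow-up visit counts as much as any on-treatment week, although study drug has been stopped for about 5 weeks by then. If baseline is also a level of the repeated factor, the mean includes a visit at which randomization makes the expected arm difference zero.

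Two things are at stake. A real on-treatment benefit may be reported as smaller than it is and tested with less power. And the estimate would blend benefit during treatment with recovery afterwards, so the overall result could not be assigned to either.

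**Working it through.** **The plan's own figure.** The 60 patients cannot be recomputed, because section 9.1.2 gives no PROMS mean or SD. It can be back-solved: 60 × 0.9 = 54 evaluable, 27 per arm. With two-sided α 0.05 (sidedness assumed) and 80% power, the standardized week-7 difference is (1.960 + 0.842) × √(2/27) = 0.762.

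**Timing.** 6 weeks − 1 week = 5 weeks, less the one taper day. With radiation ending in week 7, the follow-up score falls at about week 13. Section 4.4 also mentions a follow-up evaluation at 2 ± 1 months, so the real gap may vary.

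**Effect on the estimate.** The effect on an equally weighted mean is the average of the visit effects. Take an effect of 1 at weeks 1–7 and 0 at baseline:
- follow-up effect 0: 7/8 = 0.875; with baseline as well, 7/9 = 0.778. A flat 16% becomes 14.0% or 12.4%.
- follow-up effect 0.5: 7.5/8 = 0.938.

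**Effect on power (illustration).** Assume 80% power for the week 1–7 mean, so its non-centrality is 2.80. Let V be the variance of the mean relative to a single score. Then

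ratio = (averaged effect ÷ week 1–7 effect) ÷ √(V ÷ V₇), and power = Φ(2.80 × ratio − 1.96).

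Under compound symmetry V = (1 + (n − 1)ρ)/n. Under AR(1), V is the mean of the correlation matrix for visits at weeks 0, 1–7 and 13. With no effect at follow-up:

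| Correlation | V₇ | V₈ (+ follow-up) | V₉ (+ baseline too) | Ratio, 8 / 9 visits | Power, 8 / 9 visits |
|---|---|---|---|---|---|
| Compound symmetry 0.3 | 0.400 | 0.388 | 0.378 | 0.889 / 0.800 | 70% / 61% |
| Compound symmetry 0.5 | 0.571 | 0.563 | 0.556 | 0.882 / 0.789 | 70% / 60% |
| Compound symmetry 0.7 | 0.743 | 0.738 | 0.733 | 0.878 / 0.783 | 69% / 59% |
| AR(1) 0.7 per week | 0.518 | 0.424 | 0.400 | 0.968 / 0.885 | 77% / 70% |
| AR(1) 0.8 per week | 0.641 | 0.538 | 0.517 | 0.954 / 0.866 | 76% / 68% |
| AR(1) 0.9 per week | 0.798 | 0.713 | 0.698 | 0.926 / 0.832 | 74% / 64% |

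With no follow-up effect, these ratios do not depend on the shape of the effect over weeks 1–7.

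**If half the week-7 effect persists**, adding follow-up only:
- flat effect: 75–76% under compound symmetry and 79–83% under AR(1);
- effect rising linearly to week 7: the averaged effect is (4 + 0.5)/8 = 0.563 against 4/7 = 0.571, and power is 79–80% and 83–86%.

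So the loss is at most about 5 points and can become a gain.

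**From the plan's week-7 target instead.** Take 27 per arm, a standardized week-7 difference of 0.762, no follow-up effect and compound symmetry. Power for weeks 1–7 / plus follow-up / plus both is:
- flat effect, ρ 0.5: 96% / 91% / 83%;
- flat effect, ρ 0.8: 87% / 77% / 67%;
- linear rise, ρ 0.5: 56% / 46% / 39%.

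**The case against.** **Persistence is possible.** A reader might infer from the short half-life that no effect can remain at follow-up. The documents do not support that. Section 1.2.2 describes the mechanism as blocking receptor upregulation, and cites a retrospective series of 23 oropharyngeal patients in which gabapentin users had pain for a shorter time and feeding tubes out earlier. Nine of the ten PROMS items concern speech, eating, drinking, swallowing or taste. The half-life shows that the drug is gone, not that every benefit is. This stands, and it makes the size of the dilution uncertain.

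**The low power figures are not this trial's.** A reader might conclude that the primary test has only about 60% power. That figure needs an assumed 80% for the week 1–7 mean, compound symmetry, no follow-up effect and baseline in the mean. The plan states 80% for week 7 only, and working from that gives figures above or below 80% depending on the correlation and the course of the effect. This stands.

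**The window is ambiguous.** Section 9.1.1 introduces the 6-week score as an extra measurement and then speaks of individual weeks of the study period, so the weekly visits alone could be meant. Calling the endpoint a change also suggests baseline as a reference value. Both readings are possible, and the text settles neither.

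**Early weeks may dilute more.** With a linear rise, the week 1–7 mean is 4/7 = 57% of the week-7 effect (9.1% rather than 16%). That is a larger reduction than the follow-up visit causes, and restricting the window does not remove it.

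**A whole-course mean is a legitimate summary, and weekly results will be shown.** Both are true. But the weekly t-tests do not replace the overall test, and one follow-up score among eight or nine cannot be seen within a mean.

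**Conclusion.** The point holds as a mismatch between the primary averaging window and the trial's stated question. As most naturally read, the primary mean includes a score about 5 weeks off drug, and the wording leaves the pre-drug baseline possible as well. Baseline can only dilute the averaged effect. Follow-up dilutes it whenever its effect is below the on-treatment average.

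The size is moderate and conditional. With no follow-up effect the estimate falls by 12.5%, or by 22% with baseline. From an assumed 80%, power falls to about 69–77%, or 59–70% with baseline. With half the effect persisting, the follow-up visit costs about 5 points at most. These results assume equal visit weights and complete data; the half-persistence results also assume a flat or linear course over weeks 1–7. The documents do not show that the trial is underpowered for this reason, nor that the follow-up effect is zero. The change is still worth making, because it aligns the primary test with the trial's own question using data already planned.

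**What to change.** In section 9.1.1:
- define the primary contrast as the arm difference in mean PROMS over the weekly on-treatment visits, weeks 1 to 7;
- enter baseline PROMS as a covariate, not as a level of the averaged outcome;
- estimate the 6-week follow-up difference from the same model, as a separate secondary contrast labelled recovery after study drug.

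This is a wording change, needing no new visits, data or patients. The cost is that the primary claim no longer covers recovery, so a persisting benefit would appear only in the secondary contrast. If much of the effect does persist and correlation decays with time, the whole-period mean would have had slightly more power: in the half-persistence AR(1) cases above, up to about 3 points with a flat effect and about 6 with a linear rise.

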1.1 INTRODUCTION

1.1.1 Specific Aims

Strategies to minimize and mitigate external beam radiation therapy related mucositis and pain during the treatment of head and neck cancer remain limited. We hypothesize that gabapentin could be used to delay or reduce treatment-related pain, reliance on opioid medication, and improve the quality of life for these patients. The specific aims of this proposed study include the following:

- Evaluate the reduction or delay of mucositis related pain and morbidity with the use of gabapentin in patients with stage III or IV oropharyngeal squamous cell carcinoma undergoing definitive radiation with concurrent chemotherapy as part of their cancer management, compared to standard supportive side effect mitigation – using patient reported quality of life endpoints such as the Patient-Reported Oral Mucositis Symptoms (PROMS) scale.
- Assess morphine-equivalent opioid use in both treatment arms by collecting the patient's narcotic use in the previous 24-hour period at each weekly evaluation during radiation treatment.
- Report on change in Speech and swallow performance, as measured by the Performance Status Scale (PSS) for Head and Neck Cancer Patients.
- Evaluate changes in weight from baseline throughout treatment between the two arms.
- Calculate the proportion of patients who end up requiring a feeding tube by the end of treatment in both arms.
- Evaluate changes in patient-report quality of life using the Functional Assessment of Cancer Therapy Head & Neck (FACT-HN) and PRO-CTCAE metrics.
- Evaluate the adverse events associated with gabapentin.
- Evaluate the severity of radiation mucositis (grade 3-4, CTCAE, v. 4).

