APPENDIX III

Weekly Patient and Clinician Reported Questionnaires

Patient Reported Oral Mucositis Symptom (PROMS) Scale

1. Mouth* pain - *Mouth encompass also lips, cheeks, tongue, gums, palate and throat
no pain _____ worst possible pain

2. Difficulty speaking because of mouth* sores
no trouble speaking _____ impossible to speak

3. Restriction of speech because of mouth* sores
no restriction of speech _____ complete restriction of speech

4. Difficulty eating hard foods (hard bread, potato chips etc) because of mouth* sores
no trouble eating hard foods _____ impossible to eat hard foods

5. Difficulty eating soft foods (Jello, pudding etc) because of mouth* sores
no trouble eating soft foods _____ impossible to eat soft foods

6. Restriction of eating because of mouth* sores
no restriction of eating _____ complete restriction of eating

7. Difficulty drinking because of mouth* sores
no trouble drinking _____ impossible to drink

8. Restriction of drinking because of mouth* sores
no restriction of drinking _____ complete restriction of drinking

9. Difficulty swallowing because of mouth* sores
not difficult to swallow _____ impossible to swallow

10. Change in taste
no change in taste _____ complete change in taste

I have taken pain medication today.

Yes

No

The name of your pain medication: _____

What is the dose you are taking? _____

How do you take your pain medication? (for example, by mouth, by patch, by injection) _____

How often do you take your pain medication? (for example, once a day, twice a day)

**PERFORMANCE STATUS SCALE FOR
HEAD AND NECK CANCER PATIENTS: PSS-HN**

Patient Name _____ ID# /____/____/____/____/____/ Date /____/____/____/____/

NORMALCY OF DIET /____/

- | | |
|-----|--|
| 100 | Full diet (no restrictions) |
| 90 | Full diet (liquid assist) |
| 80 | All meat |
| 70 | Raw carrots, celery |
| 60 | Dry bread and crackers |
| 50 | Soft chewable foods (e.g., macaroni, canned/soft fruits, cooked vegetables, fish, hamburger, small pieces of meat) |
| 40 | Soft foods requiring no chewing (e.g., mashed potatoes, apple sauce, pudding) |
| 30 | Pureed foods (in blender) |
| 20 | Warm liquids |
| 10 | Cold liquids |
| 0 | Non-oral feeding (tube fed) |

PUBLIC EATING /____/

- | | |
|-----|---|
| 100 | No restriction of place, food or companion (eats out at any opportunity) |
| 75 | No restriction of place, but restricts diet when in public (eats anywhere, but may limit intake to less "messy" foods (e.g., liquids) |

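### The 80% power is for a week-7 PROMS difference, but the primary test compares mean PROMS over the whole study, and no power is given for that test

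*Combined protocol and SAP*

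**What the plan says.** Section 9.1.1 opens with "The primary endpoint is change in quality of life and pain", measured by PROMS at baseline and weekly during clinic visits. It adds: "Additional measurements will be obtained at 6-weeks (first follow-up) from the time of radiation treatment completion". The analysis is a repeated-measures ANOVA for a "difference between the mean PROMS scores of the two groups over the entire study period". The same sentence says that "t-tests will be used to examine if there was a difference in the PROMS scores for the two groups at each week" of the study, without ranking these tests against the ANOVA.

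Section 9.1.2 states that 60 patients are required to "evaluate a 16% reduction in PROMS score at week 7 (final week) of radiation treatment", at alpha 0.05 with 80% power and 10% dropout. It refers to published means and an SD but shows no values. It gives no period-average effect, no within-patient correlation and no repeated-measures calculation.

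Two other places bear on the point. Section 4.3.2 continues study drug to one week after radiation, with a one-day step-down. The first aim in Section 1.1.1 is to "Evaluate the reduction or delay of mucositis related pain and morbidity with the use of gabapentin".

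**The concern.** The sample size answers one question (do the arms differ at week 7?) and the primary test answers another (do the arms differ on average over the study?). The two have the same power only by coincidence. A reader cannot tell whether 60 patients are enough for the test that 9.1.1 puts first.

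The primary test is also not fully defined. The endpoint is called a change, but the ANOVA compares mean scores. Baseline could be averaged in, subtracted or used as a covariate. Averaging it in dilutes any effect, because baseline precedes treatment. The 6-week visit falls about five weeks after study drug ends (6 − 1 = 5), and its role is not stated. These choices change power a great deal, and as written they could be made after the data are seen.

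If the ANOVA group effect is the only primary test, type I error stays at 5%. The gap is in power and in the definition of the contrast.

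**Working it through.** **Inputs from the protocol.** N = 60, alpha 0.05, power 80% and 10% dropout (9.1.2); 1:1 allocation (4.5.1); visits at baseline, weekly during radiation and at 6 weeks (9.1.1). Seven radiation weeks follow from 9.1.2, which calls week 7 the final one, so there are 1 + 7 + 1 = 9 visits. Sidedness is not stated; I take two-sided.

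**The plan's own figure.** 60 × 0.9 = 54 evaluable, or 27 per arm. A two-sample t-test with 27 per arm has 80% power at a standardised difference of d = 0.777 (noncentral t, 52 df, noncentrality d × √(27/2)). A 16% relative reduction then implies an SD of 0.16/0.777 = 0.206, about 21% of the control mean. Without the mean and SD used, N = 60 can be neither confirmed nor refuted. I therefore hold week 7 at exactly 80% and ask what the other contrasts would have.

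**Method.** With complete data, the ANOVA group effect is a t-test on a weighted patient mean w′Y.
- Effect: 0.777 × w′(time pattern). Variance: w′Vw, in week-7 SD units.
- Nine-visit mean: weight 1/9 on each visit, 52 df.
- Mean change: mean of the eight later visits minus baseline, 52 df.
- Baseline as covariate: mean of the eight later visits, variance w′Vw − cov(w′Y, baseline)²/var(baseline), 51 df.

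**Assumptions, not from the protocol.**
- Effect at week k: linear k/7; late max(0, (k−2)/5); or constant 1. At follow-up: none, or half the week-7 effect.
- SDs: all equal to 1, or growing linearly from 0.2 at baseline to 1.0 at week 7, then 0.6 at follow-up. Growth is plausible: baseline precedes radiation, and PROMS items 2–9 in Appendix III ask about limits caused by sores, for example "Difficulty swallowing because of mouth* sores".
- Compound symmetry with correlation 0.3, 0.5 or 0.7.

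**Worked case:** correlation 0.5, linear effect, none at follow-up. The pattern averages 4/9 = 0.444 over nine visits and 4/8 = 0.5 over eight.
- Equal SDs, nine-visit mean: 0.777 × 0.444 / √0.5556 = 0.463, power 39%.
- Equal SDs, mean change: 0.777 × 0.5 / √0.5625 = 0.518, power 46%.
- Equal SDs, covariate: 0.777 × 0.5 / √(0.5625 − 0.5²) = 0.695, power 71%.
- Growing SDs, same order: 79%, 95%, 97%.

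**All compound-symmetry results** (power in %, correlation 0.3/0.5/0.7; brackets: half the effect remains at follow-up):

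| SDs | Effect | Nine-visit mean | Mean change | Covariate |
|---|---|---|---|---|
| Equal | Linear | 53/39/31 [63/47/37] | 35/46/67 [43/56/77] | 73/71/80 [82/80/89] |
| Equal | Late | 33/24/19 [43/31/25] | 22/29/44 [28/37/56] | 49/47/56 [61/59/69] |
| Growing | Linear | 91/79/68 [96/87/78] | 97/95/92 [99/98/97] | 97/97/99 [99/99/>99] |
| Growing | Late | 70/54/44 [83/68/56] | 83/77/72 [93/88/84] | 83/82/90 [93/92/96] |

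A constant effect in weeks 1–7 gives 72% to over 99% with equal SDs and over 98% with growing SDs.

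**Sensitivity, AR(1) 0.7/0.8/0.9 per week** (follow-up at week 13), covariate version, growing SDs: 92/90/93% for the linear effect and 72/68/73% for the late one. With half the effect at follow-up these become 95–97% and 80–85%. With equal SDs, late onset and no follow-up effect, power is 40–45%.

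**Week-7 difference with baseline as covariate.** Residual variance is 1 − ρ², where ρ is the correlation between baseline and week 7. At ρ = 0.5, 0.777/√0.75 = 0.897. Power is 84/90/98% under compound symmetry and 80/82/89% under AR(1), whatever the earlier time course.

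**The case against.** The best defence is that the week-7 t-test does appear in 9.1.1, in the same sentence as the ANOVA and unranked. That the ANOVA alone decides the trial is thus a reading and not an explicit statement. This is fair. But the ANOVA wording mirrors the endpoint definition, and week 7 is not singled out among the weekly tests. If week 7 was meant to decide the trial, 9.1.1 does not say so.

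Second, no loss of power is shown. Averaging visits raises power when an effect is sustained or when SDs grow. With growing SDs and compound symmetry, the covariate version has at least 82% throughout. The lowest figures need equal SDs, late onset and baseline averaged in or subtracted. This stands: the wide range reflects missing inputs, and it is not a bound, since AR(1) takes the covariate version below its compound-symmetry floor of 47%. But the plan does not say which case it assumes, and the only effect it quantifies is at the last radiation week.

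Third, all figures assume 27 patients per arm with every visit complete. A classical repeated-measures ANOVA may drop anyone with a missing visit. This is a real limit of the figures, and it does not help the stated 80%.

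Fourth, using baseline as a covariate goes beyond what is needed to reconcile the two sections. That is true, but baseline handling has to be stated anyway. In these scenarios the covariate gave at least as much power as the other two versions, to within rounding.

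**Conclusion.** The concern holds. The sample-size section and the primary analysis address different contrasts, and the stated 80% is not shown to apply to the primary test. This follows from the text alone and needs no assumption.

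The size is not determined by the protocol. With week 7 fixed at 80% and 27 complete patients per arm, the compound-symmetry scenarios run from 19% to over 99% for the nine-visit mean, 22% to over 99% for mean change, and 47% to over 99% for the covariate version. The direction is open, and I do not conclude that the trial is underpowered. What is established is that the primary contrast is not pinned down and its power is not stated. In a Phase III plan both must be settled before unblinding.

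**What to change.** In 9.1.1, name one primary contrast, with baseline PROMS as a covariate and not as an averaged outcome, and align 9.1.2 with it. There are two coherent options, and the choice is the sponsor's:

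- **(a) Week 7 as primary.** Define a longitudinal model in 9.1.1 and make its week-7 arm difference the primary contrast, two-sided 0.05, with the period average secondary. This matches 9.1.2 and needs no extra patients, provided the 9.1.2 calculation is correct; its mean and SD should be shown. The cost is that a single late visit may miss a delay in pain, which is part of the first aim.
- **(b) Period average as primary.** State which visits enter, and whether and how the off-drug 6-week visit counts. Restate the power in 9.1.2 for that test, with its SDs, correlation, time course and allowance for missed visits. The cost is that the restated power may fall below 80%.

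Under either option, label the weekly t-tests as supportive. The change is a few sentences in two sections, with no extra visits or measurements.
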